6.1.3.2. Proportion of Participants Who Develop Liver Disease Progression or Regression

6.1.3.2.1. Liver Disease Assessment Including Hepatocellular Carcinoma

Events related to liver disease progression include:

- Hepatic encephalopathy
- Hepatocellular carcinoma (HCC)
- Hepatorenal syndrome
- Hepatopulmonary syndrome
- Portopulmonary hypertension
- Hepatic hydrothorax
- Bleeding varices
- Spontaneous bacterial peritonitis
- Liver Transplant
- Ascites
- Liver-related death

Hepatic decompensation events include:

- Hepatorenal syndrome

- Hepatopulmonary syndrome
- Portopulmonary hypertension
- Hepatic hydrothorax
- Hepatic encephalopathy
- Bleeding varices
- Spontaneous bacterial peritonitis
- Ascites
- Liver-related death

Except for ascites (using data collected from liver imaging)/liver transplant/death, other events will be all collected from liver disease assessment page in eCRF. Minimal or trace ascites will not be treated as a liver event. Liver-related death will be identified by Clinical Research based on the immediate cause of death.

Participants with events related to liver disease progression that were identified prior to registry start date will be excluded from the analysis but will be listed.

Participants with De Novo HCC since registry start are defined as participants who were not identified with HCC prior to registry start and only had HCC since registry start.

Summary of participants with liver events will be provided, including the percentage of participants with events among FAS, the percentage of participants for each type of events among all the participants with events, and the percentage of participants with any event prior to registry start among FAS.

Person-time pertaining to KM analysis of time to events in this section will be calculated as: first event date (for participants who experienced events) or last day of registry (for participants who did not experience events) – registry start date + 1.

For time to first liver event since registry start, KM estimate of the proportion of participants with events related to liver disease progression, the cumulative number of participants who experienced events, were at risk, and had been censored will be summarized by treatment group and time point (Week 0, 24, 48,..., 216, and 240), where Week 0 to 216 are the exact weeks elapsed since registry start date (i.e., 0, 168, 336,..., and 1512 days), and Week 240 includes 1680 days elapsed since registry start date plus additional 30 days (i.e. 1710 days). Participants with liver events prior to registry start will be excluded from this analysis.

Same summary table as above will be provided separately for participants with De Novo HCC, with hepatic decompensation events, with liver transplant, and with all-cause death.

Same summary tables will be provided for above endpoints by baseline CTP class (CTP A, B, C, Unknown and total). Time to the first liver event and time to De Novo HCC since registry start will be summarized descriptively (n, mean, SD, median, Q1, Q3, minimum, and maximum) in a table for those participants with events occurring only during the registry study.

The KM plots will also be presented in a figure.

A by-participant, by visit listing of participants who developed above events will be provided by participant ID number in ascending order (events prior to registry start will be flagged). A separate listing will be provided for participants with De Novo HCC since registry start. Participants who experienced an HCC event more than 30 days after 240 weeks elapsed since registry start date (i.e. > 1710 days)/participants with HCC prior to registry start date will be listed separately.

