### **6.3.4. Limited Physical Exam**

The limited physical exam includes height (at Day 1 only) and weight measurements for calculation of BMI. Assessments for ascites and encephalopathy will be conducted at each visit for calculation of CTP score.

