### **6.3.5. Liver Disease Assessment**

Information will be collected at each visit for a liver disease assessment. Day 1 assessment will include determining whether any of the following have occurred since the last parent-protocol study visit prior to Day 1 for patients who achieved SVR in a Gilead-sponsored study or since the completion of the HCV therapy resulting in SVR prior to Day 1 for subjects who enroll after receiving an all-oral SOF-based regimen outside a clinical study. Assessment at all other study visits will include determining whether any of the following have occurred since the last study visit through Week 240 or early termination (unless otherwise specified). For subjects enrolled having received an all-oral SOF-based regimen outside a clinical study, the screening liver disease assessment will include the start and stop date of any clinical liver-associated events.

- Imaging of the liver performed as part of standard of care (eg, CT, MRI, or Ultrasound; results, if available)
- Liver biopsy or endoscopy to evaluate for varices (results, if available)
- Clinical liver-associated events including reports of hepatic encephalopathy, hepatocellular carcinoma, hepatorenal syndrome, hepatopulmonary syndrome, portopulmonary hypertension, hepatic hydrothorax, bleeding varices or spontaneous bacterial peritonitis
- Liver transplant (at any time prior to Day 1 and during the study)

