### **8.6.2. Secondary Analyses**

The proportion of subjects with detectable HCV RNA due to re-emergence of pre-existing virus through Week 240 will be summarized by number and percent of subjects by time point using the same model as in the primary analysis.

The proportion of subjects with detectable HCV resistance mutations through Week 240 will be summarized by number and percent of subjects by time point.

The proportion of subjects with detectable HCV RNA due to re-infection through Week 240 will be summarized by number and percent of subjects by time point.

Clinical laboratory test results related to liver disease progression or regression (ie, ALT, AST, bilirubin, albumin, platelets, PT and/or INR, and  $\alpha$ -fetoprotein) will be listed by subject. Reference ranges provided by the laboratory for each parameter will be used to evaluate the clinical significance of laboratory test results. Values falling outside of the relevant reference range will be flagged, as appropriate, in the data listings. Abnormalities in clinical laboratory test results will be summarized by enumeration of the number of subjects with values falling outside of the reference range by study day. Laboratory data will be descriptively summarized over time by study day and by the change from Baseline.

Clinical signs and symptoms related to liver disease progression or regression will be summarized by frequency and percent of subjects. Applicable clinical signs assessed include ascites, hepatic encephalopathy, varices, spontaneous bacterial peritonitis, HCC and transplant. In addition, Child-Turcotte-Pugh score will be included with the following categories, A (5-6), B (7-9), and C (10-15).

Descriptive summaries and listings will be provided for additional efficacy evaluations of the quality of life endpoints.

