6.1.3.2.3. Child-Turcotte-Pugh (CTP) Score and MELD Score

Laboratory assessment data will be used to determine the CTP score and MELD score. CTP will be calculated as a summation of all points assigned as shown in Table 6-1.

Table 6-1. Child-Turcotte-Pugh Score Calculations

Parameter	Points Assigned		
	1	2	3
Ascites	Absent	Slight	Moderate

Total Bilirubin	< 2 mg/dL (< 34.2 micromol/liter)	2 - 3 mg/dL (34.2 - 51.3 micromol/liter)	> 3 mg/dL (> 51.3 micromol/liter)
Albumin	> 3.5 g/dL (> 35 g/liter)	2.8 - 3.5 g/dL (28 - 35 g/liter)	< 2.8 g/dL (< 28 g/liter)
Prothrombin Time (Seconds over control, PT) OR International normalized ratio (INR)*	< 4 < 1.7	4 – 6 1.7 – 2.3	> 6 > 2.3
Encephalopathy	None	Grade 1 - 2	Grade 3 - 4

* INR is chosen for this study’s CTP calculation per eCRF.

A total CTP score of 5-6 is considered grade A (compensated), 7-9 is grade B (significant functional compromise/decompensated), and 10-15 is grade C (decompensated). A missing CTP score/cirrhosis status not available will be displayed as “Unknown” grade category in summaries. The proportion of participants in each CTP score category (A [5-6], B [7-9] and C [10-15]) will be summarized by visit for each treatment group. A shift table of CTP category by treatment group will be provided as well. By-participant, by-visit listing of CTP score results will be provided by participant ID number in chronological order.

MELD score will be calculated at each visit. Table with descriptive statistics (n, mean, SD, median, Q1, Q3, minimum, and maximum) for MELD score and change from baseline by visit for each treatment group will be provided. A shift table for MELD score category (\geq or <15) at each postbaseline visit from baseline will also be provided by treatment group. MELD score results will be listed by participant ID number and visit.

The MELD score will be calculated using the following formula:

$$10 \times \{[0.957 \times \text{Ln}(\text{Scr})] + [0.378 \times \text{Ln}(\text{Tbil})] + [1.12 \times \text{Ln}(\text{INR})] + 0.643\},$$

Where Scr = serum creatinine (in mg/dL), Tbil = Total Bilirubin (in mg/dL), INR = international normalized ratio, and Ln = natural log. If any lab value was less than 1.0, then it will be set to 1.0 in the calculation. If the participant received dialysis at least twice in the past week, then Scr will be set to 4.0 mg/dL in the above formula. The result will be rounded to the nearest whole number.

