6.4. Other Measurements

6.4.1. Limited Physical Exam

The limited physical exam includes height (at Day 1 only) and weight measurements for calculation of BMI. Assessments of ascites and encephalopathy will be conducted at each visit for calculation of CTP score. The results from the limited physical exam will be listed by participant ID and study visit.

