6.4.2. Liver Imaging, Biopsy, Endoscopy and Transplant

Imaging of the liver will be performed as part of standard of care (e.g., CT, MRI, or Ultrasound results, if available). Liver biopsy will be performed at any time only if results available from biopsy performed as part of standard of care. An endoscopy will be performed to evaluate for varices at any time or at Day 1 (+/- 6 months) and within 6 months prior to Week 240 visit as in protocol. Liver transplant will be reported during the study.

A shift table of varices grade from endoscopy (no varices/small varices/large varices/unknown) from Day 1 to Week 240 will be provided by treatment group and baseline CTP class (CTP A, B, C, Unknown and total).

The results of all above will be listed by participant ID number and study visit. Results of endoscopy/imaging/biopsy collected at Day 1 visit but with a procedure date before or on the most recent HCV treatment end date will be flagged in the listing.

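### Ascites counts as a liver event only through unscheduled imaging, so ascites graded at the visit examination never reaches the progression and decompensation Kaplan-Meier analyses or the prior-event exclusion

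*SAP*

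**What the plan says.** - **Event source.** SAP 6.1.3.2.1 lists ascites under both liver disease progression and hepatic decompensation. On where event data come from it says: "Except for ascites (using data collected from liver imaging)/liver transplant/death, other events will be all collected from liver disease assessment page in eCRF". It adds a severity cut: "Minimal or trace ascites will not be treated as a liver event".
- **Imaging.** Protocol 6.3.5 collects "Imaging of the liver performed as part of standard of care (eg, CT, MRI, or Ultrasound; results, if available", and SAP 6.4.2 says the same in substance. Liver imaging has no row in the procedures table of either document (Protocol Appendix 2, SAP Appendix 12.2).
- **Liver disease assessment.** The clinical liver-associated events listed in Protocol 6.3.5 include encephalopathy, hepatocellular carcinoma, bleeding varices and peritonitis. Ascites is not among them.
- **Visit examination.** SAP 6.4.1, like Protocol 6.3.4, states: "Assessments of ascites and encephalopathy will be conducted at each visit for calculation of CTP score". The examination results are otherwise only listed.
- **CTP labels.** SAP 6.1.3.2.3 calls a score of 5-6 compensated, and then: "7-9 is grade B (significant functional compromise/decompensated), and 10-15 is grade C (decompensated". CTP class is tabulated by visit and in a shift table.
- **Risk set.** SAP 6.1.3.2.1 excludes participants with liver events before registry start from the time-to-first-event analysis.
- **Protocol analysis text.** Protocol 8.6.2 says: "Applicable clinical signs assessed include ascites, hepatic encephalopathy, varices, spontaneous bacterial peritonitis, HCC and transplant". It names no data source for ascites.

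**The concern.** The registry grades ascites in every participant at every visit, but the event analysis relies on a source with no schedule. Whether ascites becomes an event therefore depends on whether an image was taken and recorded, as well as on whether the participant has ascites.

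Two parts of one primary endpoint are affected. The first is the KM proportion with a progression or decompensation event, where ascites seen on examination but not on an image goes uncounted. The second is who enters that analysis. The registry enrols participants with decompensated disease, and ascites known only from the Day 1 examination does not remove a participant from the group treated as free of earlier events.

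The baseline-CTP versions of these KM tables show the oddity most clearly. A participant can be placed in class B because of ascites on examination and still be analysed there as at risk of a first decompensation event.

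**Working it through.** The plan gives no event rate, sample size or imaging frequency, so there is no figure to reproduce. The check sets the CTP arithmetic against the event-source rule.

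**Inputs (SAP Table 6-1 and the class cut-offs).** There are five items at 1 to 3 points each. Ascites scores absent = 1, slight = 2, moderate = 3. Class A is 5-6, B is 7-9 and C is 10-15.

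**Step 1: ascites alone, other four items at the minimum (4 × 1 = 4).**

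| Ascites on examination | CTP score | Class |
|---|---|---|
| Absent | 1 + 4 = 5 | A |
| Slight | 2 + 4 = 6 | A |
| Moderate | 3 + 4 = 7 | B |

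**Step 2: no encephalopathy (1 point), all 3 × 3 × 3 = 27 combinations of bilirubin, albumin and INR points.**

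| Ascites on examination | A | B | C |
|---|---|---|---|
| Absent | 4 | 19 | 4 |
| Slight | 1 | 16 | 10 |
| Moderate | 0 | 10 | 17 |

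These count scoring patterns, not participants. Moderate ascites never leaves a participant in class A. The first row also shows that class B or C can arise from laboratory values with no ascites at all.

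**Step 3: follow the Step 1 moderate case through the event rules.** Suppose no image shows the ascites and there is no other listed event.
- Imaging route: no record, so no event.
- Liver disease assessment page: ascites is not among the events in Protocol 6.3.5, so this gives no stated second route.
- Examination: feeds the CTP score and a listing, and no rule turns either into an event.
- Result: event-free, and censored at the last day of registry in both the progression and the decompensation KM analyses. The minimal-or-trace exclusion does not explain this, because the ascites is moderate.

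**Step 4: the same case at Day 1.** Ascites found only on the Day 1 examination is not an event under the imaging rule, so the prior-event exclusion is not triggered and the participant joins the risk set.

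**Step 5: direction.**
- On-study ascites with no image and no other listed event removes an event, so the KM proportion falls.
- Baseline ascites known only from examination and imaged during follow-up is counted as new, so the KM proportion rises.

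The net effect depends on how often ascites occurs, how much is present at Day 1, how much of each is imaged, and how often another listed event follows. The documents give none of these.

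**The case against.** The strongest defence has five parts.

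1. **CTP class and clinical events are different measures.** The endpoint covers clinical and laboratory parameters, class B can come from laboratory values alone (Step 2), and the SAP's label for class B also includes functional compromise. This stands. A reader might infer that the CTP and event tables ought to agree; the documents do not require it. Ascites is the sharp case only because it is itself a listed event.
2. **The information is not lost.** The by-visit CTP table and the shift table still show a move from A to B. This also stands, but those tables correct neither the KM estimate nor its risk set.
3. **Encephalopathy is handled the same way**, graded for CTP but counted from another source. This fails. Protocol 6.3.5 names encephalopathy among the events asked about at every visit, so it has a systematic event route and ascites does not.
4. **Imaging is more specific, and the severity cut looks deliberate.** Both are fair. They support a severity threshold on examination findings and keeping the imaging-only result visible. They do not help where no image exists.
5. **The SAP may choose a data source.** A reader might infer an undeclared departure from Protocol 8.6.2. That is not supported: the protocol names ascites without a source, and Protocol 8.10 leaves further methods to the SAP.

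**Conclusion.** The gap is real and follows from the text: examination-detected ascites cannot become a progression or decompensation event, and it cannot trigger the prior-event exclusion. The change should be made, but this is a limit on ascertainment in a descriptive registry with no hypothesis tests, and the CTP tables are a partial safeguard.

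Two stronger readings are tempting and go beyond the documents.
- A reader might infer that the KM proportion is biased downward. Step 5 shows effects in both directions, so the net direction is not established.
- A reader might infer that the error varies by site or region. No imaging frequencies are given, and these KM tables are by treatment group and baseline CTP class.

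No percentage can be put on the effect from the documents. It could be nil if every case were imaged promptly. A participant whose first ascites is not imaged may still become an event later, through a later image or another listed event, so part of the effect would be delay rather than loss. The conclusion assumes that the liver disease assessment page collects the events listed in Protocol 6.3.5 and has no separate ascites field; the form itself is not in the documents.

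**What to change.** In SAP 6.1.3.2.1:

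- Derive an ascites event from imaging above minimal or trace, **or** visit-examination ascites scored Moderate (3 CTP points), dated at the earlier record.
- Apply the same rule to ascites at or before registry start. Name the Day 1 examination explicitly, since it falls on the start date and not before it.
- Report the imaging-only definition alongside.

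At minimum, keep imaging-only as the main definition, give the reason for it, and add the combined definition as a sensitivity analysis for the progression and decompensation KM tables.

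The cost is a wording change and one extra derivation from data already collected. The SAP is signed, but its introduction provides for later changes to be documented in the clinical study report. The downside is that examination is less specific than imaging, which the Moderate threshold and the parallel imaging-only result address. The threshold also leaves some class B participants without an event: slight ascites plus one laboratory item at 2 points gives 2 + 2 + 3 × 1 = 7. That is a choice of severity cut and should be stated as one.

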##### **8.2.1. Analysis Sets**

###### **8.2.1.1. Safety Analysis Set**

The analysis set includes all enrolled subjects. Both the safety and efficacy analyses will be based on the safety analysis set.

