6.5. Changes from Protocol-Specified Endpoint Analyses

No change from protocol-specified endpoint analysis is planned.

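### SAP 3.7 can date an on-registry HCC before registry start, and the SAP restricts the progression Kaplan-Meier to participants without earlier liver events while declaring no change from the protocol

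*SAP*

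**What the plan says.** **Population.** Protocol 3.1 enrols both compensated and decompensated cirrhosis. Protocol 8.2.1.1 defines the safety analysis set as everyone enrolled and adds: "Both the safety and efficacy analyses will be based on the safety analysis set". Protocol 8.6.1 plans Kaplan-Meier (KM) estimates of progression or regression and of HCC, with censoring for early discontinuation and no exclusion for earlier events. SAP 6 places the primary endpoints on the FAS.

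**Exclusion.** SAP 6.1.3.2.1 states that anyone having "events related to liver disease progression that were identified prior to registry start date will be excluded from the analysis but will be listed". For the time-to-first-liver-event KM it repeats: "Participants with liver events prior to registry start will be excluded from this analysis". It then orders further tables: "Same summary table as above will be provided separately for participants with De Novo HCC, with hepatic decompensation events", and likewise for transplant and all-cause death, all repeated by baseline CTP class. De Novo HCC cases are "participants who were not identified with HCC prior to registry start and only had HCC since registry start". A crude summary gives "the percentage of participants with events among FAS". SAP 6.5 states: "No change from protocol-specified endpoint analysis is planned".

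**Dates.** Person-time in SAP 6.1.3.2.1 runs to the "first event date (for participants who experienced events) or last day of registry", minus registry start, plus 1. SAP 3.7 imputes a missing day as 01 and a missing day and month as 01 January. An imputed death date earlier than the last available visit is moved to that visit. No equivalent rule covers HCC. Where one HCC is reported at several visits, the earliest diagnosis date is used.

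**The concern.** The date rule can make a valid on-registry HCC unusable. Its person-time may be zero or negative. If earlier-event status is read from the imputed date, the case becomes a prior HCC and leaves both the De Novo HCC and the first-liver-event analyses. HCC incidence is a primary endpoint, so each lost case matters.

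The exclusion changes who a primary-endpoint curve describes. A reader who takes SAP 6.5 at face value would think the progression KM covers the registry as enrolled, when it covers only those without an earlier event. The sole full-FAS figure for the composite is a crude percentage. That figure ignores censoring, and the SAP does not say whether excluded participants count in its numerator.

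The general exclusion sentence names no particular analysis, and the later tables are defined only by reference to the one above. Two programmers could build different denominators for De Novo HCC, decompensation, transplant and death.

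**Working it through.** **1. Partial dates, by example.** Inputs: the SAP 3.7 rule and the SAP 6.1.3.2.1 person-time formula. The dates are invented, with registry start on 20 June 2015.

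- HCC on 10 November 2015, year only recorded: imputed 1 January 2015. Person-time = -170 + 1 = -169 days (true value 143 + 1 = 144).
- HCC on 28 June 2015, day missing: imputed 1 June 2015. Person-time = -19 + 1 = -18 days (true value 8 + 1 = 9).

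**2. Partial dates, how often.** Assumption: entry uniform over a 365-day year and event uniform over the 1680 days (240 x 7) from entry, giving 365 x 1680 = 613,200 pairs.

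- Year only: the imputed date precedes registry start when the event falls in the calendar year of entry and entry is after 1 January. Count = 364 x 365 / 2 = 66,430. Share = 66,430 / 613,200 = 10.8%.
- Day missing: the same within the month of entry. Count = 7 x (31 x 30 / 2) + 4 x (30 x 29 / 2) + (28 x 27 / 2) = 3,255 + 1,740 + 378 = 5,373. Share = 0.9%.

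These are shares of partial dates, not of all HCC events.

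**3. The exclusion, side by side.**

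| | Protocol 8.2.1.1 and 8.6.1 | SAP 6.1.3.2.1, first-liver-event KM |
|---|---|---|
| Set | all enrolled | FAS without any pre-registry liver event |
| Censoring | early discontinuation | last day of registry |
| Declared as a change | - | no (SAP 6.5) |

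**4. Size of the exclusion.** The documents give no share f with an earlier event and no rate ratio RR, so only the starting level can be taken from them. T = 1710 / 365.25 = 4.682 years. Risk in event-free participants: p0 = 1 - exp(-hT).

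- HCC, 1 to 4% per year (Protocol 1.1): p0 = 4.6 to 17.1%.
- Decompensation, standing in for the composite (Protocol 1.2): 30% at 10 years gives h = -ln(0.70)/10 = 0.0357 and p0 = 15.4%; 5% at 1 year gives h = -ln(0.95) = 0.0513 and p0 = 21.3%.

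With everyone at risk the figure is (1 - f) p0 + f p1, where p1 = 1 - (1 - p0)^RR. At RR = 1 it equals p0 for any f. Purely as an assumed upper corner, f = 30% and RR = 4:

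- p0 = 15.4%: p1 = 48.7%, and the full-set figure is 0.7 x 15.4 + 0.3 x 48.7 = 25.4%.
- p0 = 21.3%: p1 = 61.7%, and the full-set figure is 0.7 x 21.3 + 0.3 x 61.7 = 33.5% (before rounding the inputs).

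The background rates describe untreated natural history, so even the starting levels are illustrative.

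**5. Scope of the exclusion.** The second exclusion sentence is tied to the first-event KM. The other tables inherit a format, with no stated risk set. If the exclusion were inherited too, a participant with earlier encephalopathy but no HCC would be removed from the HCC risk set, although the De Novo definition requires only no earlier HCC.

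**The case against.** The protocol endpoint concerns participants who develop progression, and Protocol 8.10 leaves further methods to the SAP. Restricting a first-event curve to people without an earlier event is a usual way to make that operational. The SAP states the exclusion twice, reports the percentage with any earlier event among the FAS and flags such events in the listings. This stands: the restriction is open and defensible. It does not make SAP 6.5 accurate, and it does not supply the composite for the full FAS.

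Several stronger readings are tempting but unsupported:

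- That no censoring-adjusted estimate covers the full FAS. This holds only for the composite. On the more natural reading of SAP 6.1.3.2.1, only the table layout carries over, so the death and transplant KMs run on the full FAS. Laboratory, CTP and MELD summaries also address progression and regression.
- That the exclusion biases the progression estimate. The two curves are different estimands, and nothing in the documents fixes the gap between them.
- That an early imputed date always creates a false prior HCC. The SAP speaks of events identified before registry start, and Protocol 6.3.5 collects events visit by visit, so the reporting visit could settle status. The SAP does not say which is used. The impossible person-time arises either way.
- That the classification of earlier events is distorted across treatment groups. Protocol 6.1.1 and 6.3.5 do ask parent-study and commercial entrants about different look-back periods, and SAP 5.3 only lists the liver history. Whether parent-study history is merged cannot be seen from the documents, so this is a limitation to note and no more.

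**Conclusion.** Two defects hold. The date rule is wrong as written: it permits zero or negative person-time for an on-registry HCC. The 10.8% and 0.9% figures rest on uniform entry and event dates, and the number of participants affected depends on an unknown frequency of partial dates. The progression KM departs from the protocol's population without being declared, and the composite has no censoring-adjusted counterpart in the full FAS. The size of that departure cannot be computed from the documents and is nil if earlier events do not change the rate. The unstated risk sets of the other KMs are an ambiguity to close; the documents do not show that the exclusion was meant to reach them. This should be fixed, but it does not undermine the registry.

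**What to change.** 1. **SAP 3.7.** Apply a guard to any event first reported after Day 1 whose recorded year or month is compatible with an on-registry date. Set the imputed date no earlier than the later of registry start and the last visit without the event, never outside the recorded year or month, and never after the reporting visit. If the last event-free visit lies beyond the recorded period, use registry start as the only lower bound. The upper limits are needed: without them, under the uniform dates above with visits every 168 days, an HCC reported one visit late is always dated after its true date, and 23% of year-only cases move to a later calendar year than the one recorded. Decide earlier-event status from the known date parts and the reporting visit, not the imputed date. If one HCC has a complete and a compatible partial date, use the complete one.
2. **First-liver-event KM.** Label it as event-free participants and declare the restriction in SAP 6.5. Add a companion KM of new on-registry events in the full FAS, in which an event type already recorded at Day 1 does not count as new. State that the companion still omits the 34 enrolled participants outside the FAS (SAP 3.1.2).
3. **Other KMs.** State each risk set: De Novo HCC excludes prior HCC only; first decompensation excludes prior decompensation only; all-cause death and on-registry transplant use the full FAS. State whether excluded participants count in the numerator of the crude FAS percentage.
4. **Limitation.** Note the look-back difference by entry route.

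Cost: SAP wording, at-risk flags and one more set of tables from data already collected. The companion relies on the Day 1 history, and its rates may look less favourable.
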